### 3.2 Objectives and Endpoints - Part B (PUPs/MTPs)

Objectives	Endpoints
Primary Efficacy	

 
Assess the efficacy of KOVALTRY within 48 hours of previous prophylaxis infusion in previously untreated/minimally treated Chinese children (<6 years of age) with severe hemophilia A
 
	
 
ABR within 48 hours of previous prophylaxis infusion
 

Secondary Efficacy	

 
Evaluate the efficacy of prophylaxis treatment with KOVALTRY
 
Assess the efficacy of KOVALTRY for treatment of bleeding episodes
 
Evaluate the in vivo recovery of KOVALTRY
 
Hemostatic control for minor surgeries
 
	
 
ABR during the prophylaxis period
 
Number of infusions required to treat a bleed and response to treatment of bleeds
 
In vivo recovery of KOVALTRY at baseline and study end
 
Physician assessment of adequacy of hemostasis in minor surgery
 

Safety	

 
Assess the safety of KOVALTRY for prophylaxis and treatment of bleeding episodes in previously untreated/minimally treated Chinese children (<6 years of age) with severe hemophilia A
 
	
 
FVIII inhibitor development by the Nijmegen Bethesda assay
 
Treatment-emergent adverse events (TEAEs)
 

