**Type of Participant and Disease Characteristics**

2. Chinese participants with severe hemophilia A (defined as FVIII:C <1% with one-stage clotting assay documented at the time of screening). If screening results show FVIII:C as equal to or higher than 1%, then severe hemophilia A may be confirmed by documented historical evidence from a (certified) clinical laboratory demonstrating FVIII:C <1% as determined by a one-stage clotting assay.
3. PUPs must have no previous exposure to any FVIII product.  
MTPs must have no more than 1 ED with any purified FVIII concentrate or 3 exposures with FFP or cryoprecipitate.
4. MTPs have no current evidence of inhibitor antibody as measured by the Nijmegen-modified Bethesda assay (<0.6 BU/mL) in 2 consecutive samples and must have absence of clinical signs or symptoms of decreased response to FVIII administration. Testing for the 2 negative samples must be performed by the local laboratory at least 1 week but not more than 2 weeks apart. Participants may not receive FVIII product within 72 hours prior to the collection of samples for inhibitor testing.

5. PUPs and MTPs must observe a 6-month washout period if they have received subcutaneous factor substitution therapy (emicizumab).
6. PUPs may be included if they will receive their first FVIII dose with KOVALTRY for treatment of first bleeds and agree to start prophylaxis as part of their care.  
MTPs may be included if they agree to start prophylaxis as part of their care.

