## **7.3 Efficacy Assessments**

The primary efficacy variable in Part A is the ABR of all bleeding episodes during prophylaxis. The ABR of all bleeding episodes within 48 hours of a previous prophylaxis infusion is the primary efficacy variable in Part B. The ABR of all bleeding episodes during prophylaxis in Part B and the ABR of all bleeding episodes within 48 hours of a previous prophylaxis infusion in Part A will be assessed as secondary efficacy parameters.

Additionally, the ABR for the following efficacy variables will be summarized for both Part A and Part B:

- Treated bleeding episodes
- Joint bleeding episodes
- Joint bleeding episodes within 48h of previous prophylaxis infusion
- Target joint bleeding episodes
- Spontaneous bleeding episodes
- Spontaneous bleeding episodes within 48h of previous prophylaxis infusion
- Spontaneous joint bleeding episodes
- Trauma bleeding episodes
- Trauma bleeding episodes within 48h of previous prophylaxis infusion

Other efficacy variables include:

- Minor surgery bleeding control
- Participants'/parents'/physician's (in case of surgery) assessment of the response to treatment of bleeding episodes (excellent, good, moderate, or poor)
- The number of infusions required to treat a bleeding episode
- Factor VIII usage (expressed as number of infusions and IU/kg per year, as well as IU/kg per event)
- Extent of exposure in terms of exposure days (EDs)
- Type, location, and severity of bleeding episodes
- Reason for each infusion
- Incremental recovery

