#### 9.4.1 General Considerations

There is no confirmatory comparison planned for this study; study results will be numerically evaluated and compared with the data in the completed LEOPOLD Clinical Trials.

Efficacy analyses outlined in this section only include the data from Part A or Part B (i.e., data from the Optional ITI Treatment are excluded).

For the efficacy endpoints, bleeding events will be presented as summary statistics by age groups.

The annualized bleeding rates for each participant are estimated via

$$\text{Annualized bleeding rate [per year]} = \frac{365.25 \text{ [days per year]} \times (\text{\# of bleeding episodes in treatment period})}{\text{duration of treatment period [in days]}}$$

The treatment period is defined as from the date and time of first study treatment until the date and time of last infusion of study medication, or last visit, whichever is later (not including the Optional ITI Treatment). Before this period is the screening period, after this period is the follow-up period.

Further, for the derivation of analysis variables for bleeding episodes, the following rules will apply:

- “24-hour rule”:  
No more than 1 bleeding episode in a calendar day is counted. If there is more than 1 bleeding episode in a calendar day, to determine which bleeding episodes are counted, priority is given to treated bleeding episodes, spontaneous or trauma bleeding episodes, then joint bleeding episodes. Otherwise, the first bleeding episode in the day is counted. Severity and treatment response will be the worst value of the bleeding episodes of the day. The bleeding site will be aggregated over all bleeding events from that day.
- “72-hour rule”:  
A spontaneous joint or spontaneous muscle bleeding episode will not be counted if it occurs within 72 hours of a prior bleeding episode (or infusion for that bleeding episode) at the same site. For a bleeding episode to be affected by this rule, all sites listed for the bleeding episode must be the same sites specified in the previous bleeding episode. If the current and previous bleeds are both skin/mucosa bleeds, this rule does not apply. Infusions for such bleeding episodes will be considered to be follow-up infusions.

Missing information on date and time of bleeding episodes will be substituted by the date and time of first treatment, if available.

Further handling of missing data will be described in the SAP.

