#### 9.4.3 Secondary Endpoint(s)

Spontaneous bleeding episodes, trauma bleeding episodes, joint bleeding episodes, and other bleeding episodes types will be summarized separately.

Other efficacy variables are:

- ABR of treated bleeding episodes
- ABR of target joint bleeding episodes
- ABR of bleeding episodes within 48h of previous prophylaxis infusion (total, joint, spontaneous, trauma) [for Part A]
- ABR of all bleeding episodes during prophylaxis treatment [for Part B]
- Study participant's/caregiver's assessment of response to treatment of bleeding episodes (excellent, moderate, good, or poor)
- Physician's assessment of the response to treatment of bleeding episodes in minor surgery (excellent, moderate, good, or poor)
- Evaluate proportion of patients without bleeding episodes
- The number of infusions per bleeding episode
- Factor VIII usage (expressed as number of infusions and IU/kg per year, as well as IU/kg per event)
- Incremental recovery

All details of the analysis will be provided in the SAP.

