### **4.5 Data Rules**

All bleed and infusion data will be entered into the electronic patient diary (hospital infusions will be entered into an eCRF) and imported into SAS. If an infusion is given for a bleed and the bleed information is not provided, the infusion date will be used as the bleed date. Bleeds occurring before start of prophylaxis treatment with study medication will not be counted.

Bleeding rate will be annualized using the following formula:

Annualized bleeding rate [per year] =

365.25 [days per year] x (# of bleeding episodes in treatment period) / duration of treatment period [in days]

The treatment period (exclude optional ITI period) is defined as from the date and time of first study treatment, until the date and time of last infusion of study medication, or last visit, whichever is later.

- “24-hour rule”: No more than 1 bleeding episode in a calendar day is counted. If there is more than 1 bleeding episode in a calendar day, to determine which bleeding episodes are counted, priority is given to treated bleeding episodes, spontaneous or trauma bleeding episodes, then joint bleeding episodes. Otherwise, the first bleeding episode in the day is counted. Severity and treatment response will be the worst value of the bleeding episodes of the day. The bleeding site will be aggregated over all bleeding events from that day. Regardless of which bleed is selected, the time of the first bleed in the day will be used. All other infusions in the day for treating bleeds will be considered follow-up infusions.
- “72-hour rule”: A spontaneous joint or spontaneous muscle bleeding episode will not be counted if it occurs within 72 hours of a prior bleeding episode (or infusion for that bleeding episode) at the same site. For a bleeding episode to be affected by this rule, all sites listed for the bleeding episode must be the same sites specified in the previous bleeding episode. If the current and previous bleeds are both skin/mucosa bleeds, this rule does not apply. Infusions for such bleeding episodes will be considered to be follow-up infusions.

See example below how these bleeds will be counted.

- Subject 1 reported => in analysis data set

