#### 6.2.1 Primary Endpoint(s)

The primary endpoint in Part A is the ABR of all bleeding episodes (sum of spontaneous bleeds and trauma bleeds exclude bleeding due to surgery) during prophylaxis treatment, and it will be summarized by age group ( $<12$  y,  $\geq 12$  y) separately.

The primary endpoint in Part B is the ABR of all bleeding episodes (sum of spontaneous bleeds and trauma bleeds exclude bleeding due to surgery) within 48 hours of a previous prophylaxis infusion.

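### In Part B the ABR clock starts at the first KOVALTRY dose rather than the first prophylaxis infusion, so on-demand lead-in time lowers both prophylaxis bleeding rates.

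*SAP*

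**What the plan says.** **The clock.** SAP 4.5 annualises bleeds over one treatment period: "The treatment period (exclude optional ITI period) is defined as from the date and time of first study treatment". It ends at the last infusion or last visit, whichever is later, and only ITI time is removed. Protocol 9.4.1 agrees: "The treatment period is defined as from the date and time of first study treatment until the date and time of last infusion". Neither document gives Part B its own clock. The negative binomial model in SAP 6.2.2 uses the same duration as its offset.

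**The count.** SAP 4.5 also states: "Bleeds occurring before start of prophylaxis treatment with study medication will not be counted".

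**The endpoints.** The Part B primary endpoint (SAP 6.2.1) is the ABR of bleeds "within 48 hours of a previous prophylaxis infusion". The first secondary endpoint in protocol 3.2 is "ABR during the prophylaxis period"; protocol 7.3 and 9.4.3 and SAP 6.2.2 limit it to prophylaxis in the same way.

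**Who starts on demand.** Protocol 5.1.2, criterion 6: "PUPs may be included if they will receive their first FVIII dose with KOVALTRY for treatment of first bleeds", provided that the family agrees to start prophylaxis. Protocol 6.6.2 offers an on-demand start as an alternative. Prophylaxis then follows after at most 2 to 3 bleeds, or once the child can manage weekly infusions; no limit in days is set. Protocol 7.2.2 and footnote m of the Part B schedule both provide for children who do not begin prophylaxis at Baseline.

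**The concern.** Both leading Part B efficacy endpoints are rates on prophylaxis, but the time base can include time off prophylaxis. Within SAP 4.5 the numerator starts at the first prophylaxis infusion and the denominator at the first dose. Where these dates differ, the extra days cannot contribute a bleed.

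The error runs one way. An affected child with any counted bleed reads too low, a child with none stays at 0, and no child reads too high. In a single-arm study whose results are compared numerically with LEOPOLD, that favours the product. With about six children, each carries about a sixth of the mean that will be set beside 1.9 from LEOPOLD Kids Part B. An interim cut for licence renewal (protocol 9.5) could shorten prophylaxis follow-up and so raise the diluted share.

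**Working it through.** **Planning inputs.** Protocol 9.2.2 and SAP 3.1.2 give a 48-hour ABR with mean 1.9 and SD 3.3, and n = 6. They state a probability above 80% that the six-patient mean is below 2.9. With one-year negative binomial counts, the size parameter is 1.9²/(3.3² − 1.9) = 3.61/8.99 = 0.402. The sum over six patients then has size 6 × 0.402, and P(sum ≤ 17) = 0.807. The plan's figure reproduces, so its mean and SD are used below.

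**Dilution.** Let P be time on prophylaxis and L the time from first study dose to first prophylaxis infusion. The count is the same on both clocks, so

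reported ABR = ABR on prophylaxis × P/(P + L), and the shortfall is L/(P + L).

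- P: 6 to 12 months, the range protocol 7.2.8 expects for most children.
- L: not given. Assumed 1 to 3 months, with 2 weeks as a short case and 6 months as a stress case.
- k, the number of affected children: not given, so taken from 0 to 6.

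| L | P = 12 months | P = 6 months |
|---|---|---|
| 0.5 month | 0.5/12.5 = 4.0% | 0.5/6.5 = 7.7% |
| 1 month | 1/13 = 7.7% | 1/7 = 14.3% |
| 3 months | 3/15 = 20.0% | 3/9 = 33.3% |
| 6 months | 6/18 = 33.3% | 6/12 = 50.0% |

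**Primary endpoint.** A bleed before the first prophylaxis infusion cannot fall within 48 hours after one, so the numerator is already right and only the clock dilutes the rate. If every child has an ABR of 1.9 on the prophylaxis clock, the six-child mean falls by 1.9 × (k/6) × L/(P + L). For L = 1 to 3 months:

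- k = 0: 0
- k = 1: 0.024 to 0.106
- k = 3: 0.073 to 0.317
- k = 6: 0.146 to 0.633

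The standard error of the mean is 3.3/√6 = 1.35. One affected child therefore shifts the mean by about 2% to 8% of a standard error; the extreme of 0.633 is 47% of one.

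**Secondary endpoint.** For a child with 2 counted bleeds on prophylaxis:

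- P = 6, L = 3 months: 2/0.75 = 2.67 per year as written, against 2/0.50 = 4.00 on the prophylaxis clock.
- P = 12, L = 1 month: 2/1.083 = 1.85 against 2/1.00 = 2.00.

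**The case against.** **The rule may be refined elsewhere.** SAP section 1 makes a separate Analysis Datasets document an integral part of the SAP, and a derived start date could be defined there. That document is not available here. If it does use the prophylaxis date, it contradicts SAP 4.5, which would still need correcting.

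**The larger figures are a corner case.** A long lead-in is most likely in a child waiting to be large enough for weekly infusion. At one infusion a week, 50 exposure days take about 50 weeks, or 11.5 months. With L = 3 the shortfall is then 3/14.5 = 21%, and the six-child mean falls by about 0.07 with one child affected. This stands: 33% needs roughly twice-weekly dosing after a three-month lead-in. All six affected is also remote, because protocol 7.2.2 gives minimally treated children their first dose at Baseline and foresees delayed prophylaxis only for previously untreated children.

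**The 48-hour ABR is a convention anyway.** On weekly dosing, 120 of every 168 hours (71%) of prophylaxis time lies outside the 48-hour windows, yet all of it is in the denominator. Removing the lead-in does not turn this into a rate over time at risk. That is fair, and the mismatch is cleaner for the secondary endpoint. It does not justify adding time before any prophylaxis infusion was given.

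**Changing the SAP alone departs from protocol 9.4.1**, and the protocol wanted the SAP final before the first visit because the trial is open-label. Also, the clock used in LEOPOLD Kids Part B is not shown, so a new main figure might be less comparable with 1.9. These points affect how the change is made and reported, not whether the definition is right.

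**Conclusion.** The concern holds: the Part B denominator is wrong as written for children who start on demand. The direction is certain from the text, downward or unchanged and never upward. The size is not, because neither the lead-in length nor the number of on-demand starters is given. Under the assumed lead-in of 1 to 3 months, an affected child with a counted bleed reads 8% to 33% low. Children whose first dose is prophylaxis are unaffected.

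The shift in the group mean is well inside sampling error, and the study is descriptive with no test or decision rule resting on it. This is a definition that should be corrected, not a threat to the study. Sampling error is still no reason to keep a known one-directional error in a primary endpoint when the correction is simple.

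**What to change.** **SAP 4.5.** Add that, for Part B, the ABR period starts at the first regular prophylaxis infusion, for both bleeds and time. Use the same start for the negative binomial offset in SAP 6.2.2 if that model is applied to Part B.

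**Defining the date.** Take the earlier of:

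1. the first diary infusion with the reason Prophylaxis (not Unscheduled prophylaxis);
2. the CRF-recorded in-hospital infusion that starts prophylaxis.

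Protocol 7.3.1 lists a reason only for diary infusions, and surgery infusions also go to the CRF (protocol 10.4), so item 2 needs care. It can be identified because protocol 7.2.2 ties the first recovery sample to the start of prophylaxis, and protocol 7.3.1 sends a visit infusion given for a bleed to the diary.

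**Reporting.** List on-demand time and bleeds separately. Keep the ABR on the current clock as a supportive row, so that the LEOPOLD Kids Part B comparison can be read either way.

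**Cost.** One sentence and one derived date from data already collected. Log the change and its reason in SAP section 7, and align protocol 9.4.1 at the next amendment; until then the departure should be stated openly. The SAP needs revision in any case: it is based on protocol version 2.0 and still allows the combined screening and baseline visit that Amendment 2 removed. The price is a slightly less favourable ABR for affected children.

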## Statistical Analysis Plan

BAY 81-8973 (KOVALTRY) / 19855

Page: 9 of 15

- Day 5 spontaneous bleed in right knee => bleed as reported
- Day 7 spontaneous bleed in right knee => follow-up infusion
- Day 9 spontaneous bleed in right knee => follow-up infusion
- Day 11 spontaneous bleed in right knee => follow-up infusion

○ Subject 2 reported => in analysis data set

- Day 5 spontaneous bleed in right knee => bleed as reported
- Day 7 follow-up infusion => as reported
- Day 9 follow-up infusion => as reported
- Day 11 spontaneous bleed in right knee => follow-up infusion

Under the 72 hour rule, both subjects will have 1 spontaneous bleed and 3 associated follow/up infusions.

Missing information on date and time of bleeding episodes still be substituted by the date and time of first treatment, if available.

When sorting the infusion records for counting number of infusions associated with each bleed, 1st infusions for bleeds will use the bleed date (if missing then use the infusion date). Follow-up infusions will use the dose date.

Joint bleeds can occur in more than 1 joint site. For each joint bleed, count all sites (combining left and right). For the table showing the Joint Site frequency, sum counts over all sites.

### 4.6 Validity Review

The results of the final data assessment will be documented in the final list of important deviations, validity findings and assignment to analysis set(s). Any changes to the statistical analysis prompted by the results of the review of study data will be documented in an amendment and, if applicable, in a supplement to this SAP.

## 5. Analysis Sets

### 5.1 Assignment of analysis sets

Final decisions regarding the assignment of subjects to analysis sets will be made during the review of study data and documented in the final list of important deviations, validity findings and assignment to analysis set(s) (see section 4.6).

#### Enrolled population

All participants who signed the ICF or had an ICF signed on their behalf by a parent or legal representative

#### Modified Intent-To-Treat (mITT)

All study participants who have infusion/bleeding data from the EPD and/or CRF will be included in mITT. The mITT population will be used for the efficacy analysis.

The ITT is inclusive of all enrolled and eligible patients. Modified ITT was introduced for this study as there is an additional condition that is to be met for participants included in ITT. This

## Statistical Analysis Plan

BAY 81-8973 (KOVALTRY) / 19855

Page: 10 of 15

condition is that study participants need to have infusion/bleeding data from the EPD and /or CRF.

Therefore, ITT analysis population is renamed “modified ITT” for this study.

### **Safety analysis set (SAF)**

Participants enrolled into the study and received at least 1 dose of study drug will be included in the SAF. The safety population will be used for the safety analysis.

### **Per protocol set (PPS)**

All mITT participants, who completed study treatment and have at least 50 exposure days on study, without important protocol deviations significantly impacting efficacy endpoints will be included in PPS. The detailed definitions and the assignment of subjects to this analysis set will be based on the validity review meeting.

The PPS population will only be used for the efficacy analysis if at least 5% of mITT participants (<12 or  $\geq$ 12 years of age) are excluded. The PP population is only in Part A; Part B will not have a PP population.

Exposure days refers to days with at least one infusion of study drug.

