## 6.6 Dose Modification

### 6.6.1 Dose Modification in Part A (PTPs)

Dosing recommendations for prophylaxis in adults/adolescents and children are provided as per the approved label. Dose modifications should be individualized based on clinical response at the investigator discretion.

Study participants receiving prophylaxis treatment 2x per week (i.e., on a 2x/week prophylaxis regimen) should increase prophylaxis dosing frequency to three times per week if they experience 2 or more spontaneous joint and/or muscle bleeding episodes within a 6-week period.

Study participants receiving prophylaxis treatment 3x per week (i.e., on a 3x/week prophylaxis regimen) should increase prophylaxis dosing frequency to every other day if they experience 2 or more spontaneous joint and/or muscle bleeding episodes within a 6-week period.

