### **6.6.3 Breakthrough Bleeds and Minor Surgery**

KOVALTRY will also be used for the treatment of bleeding episodes in this study. The dose should be individualized according to severity of the specific bleeding episode.

KOVALTRY will also be used for perioperative management of minor surgery that may occur during the course of the study.

The dosages used for treatment of breakthrough bleeds or minor surgery will be at the discretion of the investigator.

A guide for dosing for bleeding episodes and surgery, as well as a guide for the assessment of adequacy of hemostasis during surgery, are provided in Section [10.4](#).

Definitions of response to treatment of breakthrough bleeds (i.e., excellent, good, moderate, or poor [or none]) is provided in Section [7.3.1](#).

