#### Infusion of KOVALTRY

For each self-administered infusion of KOVALTRY, information must be recorded on the EPD as follows:

- a. Date and time
- b. Individual vial number (bar code scan from vial label or manual entry) and units administered
- c. Reason for treatment:
  - Prophylaxis
  - Unscheduled prophylaxis (e.g., for physical activities, suspected or non-evident bleeding following identified trauma)
  - Spontaneous bleeding first treatment
  - Trauma bleeding first treatment
  - Follow-up treatment
  - Surgery
  - ITI (only applicable to participants who develop high-titer inhibitor and received ITI)

Infusions of KOVALTRY as part of protocol mandated visits and procedures (e.g., for recovery and PK) will be recorded on the respective CRF pages.

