#### ❖ Routine Prophylaxis

##### Adolescents and Adults

A total of 140 subjects were treated with KOVALTRY for at least 12 months with median (range) 157 EDs (25–178) in Study 1, [305 EDs (25–355) inclusive of extension phase], and 153 EDs (103–187) in Study 2 (see Table 8). In both studies, subjects in the Intent-to-Treat (ITT) population received 95% to 100% of the prescribed number of prophylaxis infusions.

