**Children 12 Years of Age and Younger**

A total of 51 PTPs were treated with KOVALTRY for at least 6 months with median (range) 73 EDs (37-103) (see Table 10). Subjects received >95% of the prescribed number of prophylaxis infusions.

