**Table 14: Prophylaxis Treatment with KOVALTRY in Adolescents and Adults – Treatment Exposure**

	China subgroup (N = 17a)	
Median nominal prophylaxis dose/ infusion (range)	All Prophylaxis, 2 times per week, low dose Prophylaxis, 3 times per week, high dose	31.69 IU/kg (21.5-41.9 IU/kg) 30.42 IU/kg (21.6-32.0 IU/kg) 40.41 IU/kg (30.7-41.9 IU/kg)
Treatment duration		1 year

a: 2 times per week (n=7); 3 times per week (n=10)

Comparison of the bleeding rates between subjects receiving on-demand therapy versus prophylaxis in an ANOVA demonstrated a statistically significant difference ( $p<0.0001$ ) in the median ABR in subjects receiving on-demand therapy (63.54 bleeds per year) as compared to subjects receiving prophylaxis (1.98 bleeds per year). Mean ABR in subjects receiving on-demand therapy was  $71.93 \pm 22.96$  versus  $3.91 \pm 4.79$  in the subjects receiving prophylaxis.

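### The Part A per-protocol set counts bleed-treatment days towards its 50-exposure-day rule, so entry for twice-weekly participants depends partly on bleeding

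*SAP*

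**What the plan says.** The per-protocol set, used in Part A only, is described in SAP 5.1 as "All mITT participants, who completed study treatment and have at least 50 exposure days on study", without important deviations affecting efficacy. Protocol Table 9-1 carries the same 50-day condition. The SAP adds: "Exposure days refers to days with at least one infusion of study drug". No reason for infusion is left out of the count.

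Three other places feed that count:
- Protocol 6.6.3: "KOVALTRY will also be used for the treatment of bleeding episodes in this study".
- Protocol 6.6.1: participants on twice-weekly dosing "should increase prophylaxis dosing frequency to three times per week if they experience 2 or more spontaneous joint and/or muscle bleeding episodes" within six weeks.
- Protocol 7.3.1 lists further infusion reasons, among them surgery and "Unscheduled prophylaxis (e.g., for physical activities, suspected or non-evident bleeding following identified trauma").

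Twice-weekly prophylaxis is allowed in both age groups. The primary and secondary analyses are repeated in this set if at least 5% of mITT participants in an age group fall outside it. SAP 5.1 leaves detailed definitions and assignment to the validity review meeting.

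**The concern.** A per-protocol repeat should show what happens among participants who followed the plan. Completion of treatment is already a separate entry condition, so the 50-day count acts as an adherence test. It is an uneven one. At three times weekly, about 78 infusions are scheduled and 64% adherence passes. At twice weekly almost every dose is needed. A twice-weekly participant who misses four of 53 doses and never bleeds has 49 exposure days and is dropped. The same participant with one bleed treated on a non-prophylaxis day has 50 and is kept. The bleed-driven step-up in frequency works in the same direction.

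Membership then depends partly on the outcome being summarized. A difference between the per-protocol and mITT ABR could come from the entry rule and not from adherence. The rule can also trigger the repeat by itself: 5% of 30 is 1.5 and 5% of 12 is 0.6, so two children (6.7%) or one adolescent/adult (8.3%) is enough.

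**Working it through.** **The plan's own figure.** Children, SD 5, n = 30: 1.96 × 5/√30 = 1.79. This reproduces the stated half-width of 1.8 (2.2 to 5.8 around 4). The 50-day threshold has no stated derivation.

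**Scheduled infusions, twice weekly.** Six months is 182.6 days, with a final-visit window of ±7 days. Intervals: 2 × 175.6/7 = 50.2; 2 × 182.6/7 = 52.2; 2 × 189.6/7 = 54.2. KOVALTRY is given in hospital at both Visit 2 and Visit 5 (Protocol 7.1.2, 7.1.5), so one dose is added: about 51, 53 and 55. The margin over 50 is 1, 3 or 5 days.

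**Inputs.**
- Children's ABR: mean 4, SD 5 (SAP 3.1.1). Half-year bleeds are negative binomial with mean 2, variance 6.25, k = 2²/(6.25 − 2) = 0.941.
- Twice-weekly share: (9 + 13)/51 = 22/51 = 43%, the starting regimens in the earlier paediatric study (package insert, Table 10). Its use here is an assumption.
- Adherence: the insert reports for children "Subjects received >95% of the prescribed number of prophylaxis infusions" and for adolescents and adults "received 95% to 100% of the prescribed number of prophylaxis infusions". I use 95%, 97% and 99%.
- Further assumptions: one infusion per bleed; 5/7 of these on non-prophylaxis days; the three site doses (Visits 2, 4, 5) always given; bleeding independent of adherence; participants on other regimens all qualify.

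**Formula.** With n scheduled infusions, misses are Bin(n − 3, 1 − adherence) and credit days are Bin(bleeds, 5/7). A participant qualifies if n − misses + credit ≥ 50. With P the twice-weekly proportion kept:

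arm ABR = (0.431 × P × ABR of those kept + 0.569 × 4)/(0.431 × P + 0.569)

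**Nominal case, 53 infusions, 95% adherence.** With no bleeds, the chance of qualifying is P(Bin(50, 0.05) ≤ 3) = 76%. With three or more bleeds it is 98%. Overall P = 0.868; ABR is 4.43 in those kept and 1.19 in those dropped. Arm ABR = (0.431 × 0.868 × 4.43 + 0.569 × 4)/(0.431 × 0.868 + 0.569) = 4.17. Share of the arm dropped: 0.431 × (1 − 0.868) = 5.7%.

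**Children's arm, true ABR 4.0.**

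| Adherence | PP ABR at 55 / 53 / 51 infusions | Chance the rule alone drops at least 2 of 30 |
|---|---|---|
| 95% | 4.03 / 4.17 / 4.57 | 3.5% / 51% / 98% |
| 97% | 4.00 / 4.04 / 4.31 | under 0.1% / 6% / 81% |
| 99% | 4.00 / 4.00 / 4.06 | not tabulated |

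**Adolescents/adults.** The insert's China subgroup gives "2 times per week (n=7); 3 times per week (n=10"), a twice-weekly share of 7/17, with ABR 3.91 (SD 4.79). At 53 infusions the rule alone drops at least 1 of 12 with probability 49% at 95% adherence and 14% at 97%.

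**Sensitivity at 53 infusions, 95%.** An assumed mean of one unscheduled-prophylaxis day per participant (the documents give no rate) lowers 4.17 to 4.09. If each missed dose multiplied the bleed rate by 1.5, it would be 4.11. The step-up in frequency is not modelled; it would add to the effect.

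**The case against.** The strongest reply is that the effect is small where the data are likely to lie. Earlier paediatric adherence was above 95%, so the 95% row is the edge of the documented range. At the nominal 53 infusions the shift is 0.17, 0.04 or 0.00, about 9%, 2% or 0% of the 1.8 half-width. The larger figures need an early final visit as well. The study tests no hypothesis, and triggering the repeat only adds a supportive table. All of this stands, and it sets the size of the point.

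A second reply is that the validity review can settle the definitions, with changes documented under SAP 4.6. That leaves room to refine the rule, but the 50-day condition stands as written, and a refinement made at that meeting would follow review of open-label data.

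Three stronger readings are tempting and are not supported:
- That the margin can be zero. This follows from counting intervals alone; with doses at both end visits it is 1 to 5 days.
- That bleed-free twice-weekly participants cannot qualify. At 53 infusions and 95% adherence, 76% of them do.
- That the primary result is biased or the product flattered. Efficacy rests on mITT, which has no exposure-day condition, and dropping low bleeders raises the per-protocol ABR.

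**Conclusion.** The point holds as a modest design weakness in a supportive analysis. Per-protocol entry depends partly on bleeding for twice-weekly participants, and the texts alone establish this. Its size rests on the assumed regimen mix, adherence, placement of bleed infusions and independence of bleeding from adherence. On those assumptions the children's per-protocol ABR is raised by up to 0.17 at the nominal schedule and by up to 0.57 at the early edge of the visit window with 95% adherence. Near 99% adherence it is negligible at the nominal schedule. Worth considering; it is no obstacle to the primary analysis.

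**What to change.** In SAP 5.1 and Protocol Table 9-1, replace the 50-day condition with completion of treatment plus a prophylaxis-compliance threshold based on the SAP 6.1.2 formula. The sponsor chooses the cut-off and fixes it in the SAP before data review. State that the bleeding and surgery exclusion applies to both numerator and denominator, which 6.1.2 leaves unclear. Keep 50 exposure days as a descriptive count.

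This removes the direct credit for bleed-treatment days. A small residual dependence remains, because doses missed straight after a bleed are left out for bleeders and counted for others. For scale only, and ignoring that exclusion: at 53 infusions and 95% adherence, a 90% cut-off allows five misses and drops P(Bin(50, 0.05) > 5) = 3.8% of twice-weekly participants; an 80% cut-off allows ten and drops under 0.01%.

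No new data are needed. The cost is wording, giving up a round number, and justifying a cut-off in advance.

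Minor: Table 9-1 and SAP 5.1 admit participants with diary and/or CRF data, while Protocol 9.4.2 speaks of excluding those without diary data. Bleeds are recorded in the diary and protocol-visit infusions in the CRF, so reconcile the texts so that time without diary data is not counted as bleed-free. The number affected is unknown and probably small.

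Editorial: SAP 6.2 words the trigger as exclusion from mITT; word it as exclusion from the per-protocol set, as SAP 5.1 does.
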